- ^a The week 52 visit must occur on or after the 1-year anniversary of Study Day 1 in the parent study. The timing of the visit should also be at least 28 weeks (± 10 days) from the actual date of the Week 24/Baseline visit.
- ^b Unscheduled visits may be conducted at the investigator's discretion when needed. The reason for the visit will be captured in the source documents.
- ^c The Follow-up visit may be waived if the patient enrolls directly into another relugolix clinical study upon completion of the Week 52 visit.
- ^d May be signed up to 30 days prior to the Week 24/Baseline visit or during the Week 24/Baseline visit. Enrollment in MVT-601-3003 is defined by administration of the first dose of MVT-601-3003 study drug.
- ^e Record all prescription and nonprescription drug and supplements taken from the Week 24/Baseline visit through the Safety Follow-Up period. Concomitant medications with start date prior to the first dose of study drug for MVT-601-3003 should be reported as concomitant medications in the parent study (MVT-601-3001 or MVT-601-3002). Concomitant medications initiated during the MVT-601-3001 or MVT-601-3002 studies and ongoing at the time of the first dose in Study MVT-601-3003 will be recorded in the electronic case report form.
- ^f Concomitant medications are recorded both for the parent study and for MVT-601-3003 at the Week 24/Baseline visit. (See footnote c for further details).
- ^g This is a parent study (MVT-601-3001 or MVT-601-3002) Week 24 procedure that serves as the Week 24/Baseline procedure for MVT-601-3003 and is covered under the informed consent for the parent study.
- ^h The indicated procedure may be performed at the Unscheduled visit based on the purpose of the visit (eg, follow-up for an adverse event or abnormal laboratory test).
- ⁱ See parent study protocols (MVT-601-3001 or MVT-601-3002) for instructions on testing visual acuity.
- ^j The exam may include a gynecologic examination, if indicated based on signs and symptoms.
- ^k The 12-lead ECGs will be submitted for central reading.
- ^l Clinical laboratory tests at each visit include clinical chemistries and a complete blood count. At the Week 24/Baseline visit and Week 52 visit, additional tests include: fasting (at least 8 hours) glucose, lipid profile, and hemoglobin A1c.
- ^m Samples should be obtained in a fasted state (at least 8 hours). Water is allowed during the fasting period.

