Study drug compliance will be reviewed at each visit.

Fasting (other than water) for at least 8 hours is required prior to blood sampling on Week 24/Baseline and Week 52/Early Termination visits and for 1 hour after administration of the study drug in the clinic. Laboratory requisitions must indicate whether or not the patient was not fasted for their chemistry and lipid testing.

Refer to the Schedule of Activities (see Section 1.1) for information about study procedures during the Open-Label Treatment period.

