6.6.2.4. Clinical Laboratory Samples

All protocol-required laboratory assessments must be conducted in accordance with the Study Reference Manual and the protocol Schedule of Activities (see Section 1.1). Laboratory requisition forms must be completed and samples must be clearly labelled with the Patient Identification Number, protocol number, site/center number, and visit date. Details for the preparation and shipment of samples will be provided. Reference ranges for all safety parameters will be provided to the site by the central laboratory. The samples collected for clinical laboratory tests are listed in [Table 4](#).

Table 4: Clinical Laboratory Tests

Chemistry	Hematology	Urinalysis
Potassium Chloride Bicarbonate Blood Urea Nitrogen Creatinine Glucose Calcium Phosphate Magnesium Sodium Albumin Creatinine Kinase Hemoglobin A1c Creatine Kinase Bilirubin Total Alanine Aminotransferase Aspartate Aminotransferase Gamma-Glutamyl Transferase Alkaline phosphatase	White Blood Cell (WBC) Count WBC Differential Red Blood Cell Count Hemoglobin Hematocrit Mean Corpuscular Volume Platelet Count RBC morphology	Protein Glucose Blood Urobilinogen Bilirubin Color and Clarity pH Leucocyte Esterase Ketones Nitrite Specific Gravity Urine Microscopy (reflex testing based on abnormal urine analysis)
	Lipids	Pregnancy
	Total Cholesterol Low Density Lipoprotein High Density Lipoprotein Triglycerides	Pregnancy test (human chorionic gonadotropin)
Hormones		
Estradiol		

The central laboratory will perform laboratory tests for chemistry, hematology, urinalysis, serology, and plasma and serum hormone levels. Each study site will conduct urine pregnancy tests locally.

All laboratory tests with values that are considered abnormal and clinically significant during participation in the study or within 28 days after the last dose of study drug should be repeated until the values return to normal, baseline, or have stabilized. Abnormal and clinically significant results should be reported as adverse events.

The investigator will maintain a copy of the reference ranges (with the record of the reference ranges) for the laboratory or laboratories used.

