QTc Prolongation Negative Thorough QT/QTc clinical study.	Empiric exclusion of baseline QTcF > 470 msec in the parent studies.	12-lead ECG at the Week 24/Baseline and Week 52/Early Termination visits, and as clinically applicable; withdrawal for QTcF > 500 msec.
Hepatic Enzymes Isolated increases in hepatic transaminases have been observed in prior clinical studies. There have been no reported cases consistent with drug-induced liver injury including an increase in bilirubin. Abnormal liver test results are considered adverse events of clinical interest in this study.	Exclusion criteria for AST and ALT > 2 x the ULN; total bilirubin values > 1.5 x ULN	Abnormal liver test results (AST or ALT > 3 x ULN) that develop during the Open-Label Treatment period will be reported within 24 hours of study personnel awareness.

Potential Risk of Clinical Significance	Mitigation Strategy	
	Impact on Eligibility	Monitoring and Withdrawal Criteria

Phospholipidosis
 
Data from nonclinical studies in rats and monkeys showed histopathological changes consistent with PLD. PLD by itself is not adverse. No clinical evidence of relugolix-related PLD-associated toxicity has been observed nor was there a clinically meaningful increase in a biomarker of PLD assessed in phase 2 clinical studies.
	
Patients with significant underlying medical conditions are excluded.
	
Routine safety monitoring including laboratory assessments, ECGs, and assessment of adverse events, including any ophthalmologic adverse events, will be monitored during this study.

Metabolic Changes
 
Metabolic changes (insulin resistance, dyslipidemia, and increased weight) with increased risk of diabetes are a potential risk of the hypoestrogenic state induced by relugolix.
	
Exclusion criteria for current medical history of cardiovascular disease in the parent studies.
	
Fasting lipids and glucose will be monitored during the study.

Reproductive Toxicity
	
Premenopausal compliance with specified acceptable non-hormonal contraception; exclusion of pregnant and lactating women.
	
Pregnancy testing at each study visit; immediate withdrawal for pregnancy.

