4.3.8. Visit Windows

Visit windows, which will be used to associate assessments with a scheduled visit, will be used only for summarizing data by visit. The windows for scheduled assessments are shown in [Table 2](#), [Table 3](#) (BMD), [Table 4](#) (electrocardiogram [ECG]), [Table 6](#) (UFS-QoL), and [Table 6](#) (transvaginal ultrasound and EQ-5D-5L) respectively. For safety assessments, the study day will be used to determine the associated visit window. There will be no separation of data from the parent and extension study. For example, if an assessment in the extension study falls in the Week 24 visit window, it will be summarized as Week 24.

If the results from more than one assessment are within a given visit window, the non-missing result from the assessment closest to the target date will be used. If two assessments are equally close to the target day, the earlier assessment will be used. For summaries of shift from Baseline in safety parameters, all values will be considered for these analyses.

Table 2: Visit Windows for Monthly Assessments

Visit	Start Day	Target Day	End Day
Week 4 ^a	1	29	43
Week 8	44	57	71
Week 12	72	85	99
Week 16	100	113	127
Week 20	128	141	155
Week 24	156	169	183
Week 28	184	197	211
Week 32	212	225	239
Week 36	240	253	267
Week 40	268	281	295
Week 44	296	309	323
Week 48	324	337	351
Week 52	352	365	Date of last dose + 6 ^b
Safety Follow-Up ^c	Date of last dose + 7 days	Date of last dose + 30 days	Date of last dose + 60 days

^a Start day of Week 4 for study day 1 includes only post-Baseline assessments that occurred after the first dose.

^b End day of Week 52 is date of last dose + 1 for patients entering the MVT-601-035 study.

^c The safety follow-up visit window will be restricted to assessments prior to the date of initiation of another investigational agent or hormonal therapy affecting the hypothalamic-pituitary-gonadal axis or surgical intervention for uterine fibroids.

Table 3: Visit Windows for Bone Mineral Density Assessments

Visit	Start Day	Target Day	End Day
Week 12	64	85	106
Week 24	148	169	196
Week 36	197	253	308
Week 52	309	365	421

Assessments will be excluded from analysis if they occur on or after the date of initiation of another investigational agent or hormonal therapy affecting the hypothalamic-pituitary-gonadal axis or surgical intervention for uterine fibroids. Assessments after date of last dose of extension study drug + 30 days will also be excluded from analysis.

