9.2. Laboratory Data

Laboratory parameters, including chemistry and hematology panels, specified as per protocol for the parent and extension studies, and collected from the central laboratory will be tabulated and presented in by-patient listings. Urinalysis and hepatitis virus serological test results will be provided in by-patient listing only.

The National Cancer Institute CTCAE Grading Scale with numeric component will be used to categorize toxicity grade for laboratory parameters (CTCAE v5.0, dated 27 Nov 2017). Parameters that have criteria available for both low and high values (eg, hypercalcemia for a high value of calcium and hypocalcemia for a low value of calcium) will be summarized for both criteria (low and high). Patients will only be counted once for each criterion. The same patient can be counted for both criteria if she has laboratory values meeting each criterion. Shift tables will be provided for each gradable parameter to summarize Baseline toxicity grade versus worst post-Baseline toxicity grade throughout the parent and extension studies. For laboratory parameters that are not gradable by the CTCAE, a shift table based upon the normal range (low,

normal, and high) will be provided for each parameter to summarize the Baseline versus worst post-Baseline results throughout the parent and extension studies.

Boxplots of laboratory values over time, including visits in both the parent study and extension study, will be plotted for key laboratory parameters. These laboratory parameters include, but are not limited to, hematology (hemoglobin, platelets, leukocytes, neutrophils), creatinine, glomerular filtration rate, and hepatic function panel (alanine aminotransferase [ALT], aspartate aminotransferase [AST], alkaline phosphatase [ALP], and total bilirubin).

The change from Baseline to each post-Baseline study visit will be presented by parent study treatment group for each laboratory test in both tables and figures.

The number and proportion of patients with liver test elevations will be presented by parent study treatment group. Liver test elevations are assessed by using post-Baseline results for ALT, AST, ALP, and total bilirubin based on the definitions presented in [Table 13](#).

Table 13: Categories of Liver Test Elevations

Laboratory Test	Category
ALT or AST	ALT or AST > ULN < 3 × ULN ALT or AST ≥ 3 × to < 5 × ULN ALT or AST ≥ 5 × to < 10 × ULN ALT or AST ≥ 10 to < 20 × ULN ALT or AST ≥ 20 × ULN

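### SAP 9.2 mixes fasted and possibly unfasted glucose in its by-visit and worst-value summaries, and the fasting-glucose shift in Appendix 1 stops at Week 24, omitting Week 52

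*SAP*

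**What the plan says.** **Analysis (SAP).** Section 9.2 applies one by-visit rule to every test: "The change from Baseline to each post-Baseline study visit will be presented by parent study treatment group for each laboratory test". For tests with CTCAE grades, the shift tables "summarize Baseline toxicity grade versus worst post-Baseline toxicity grade throughout the parent and extension studies". For the rest, a low/normal/high table "will be provided for each parameter to summarize the Baseline versus worst post-Baseline results throughout the parent and extension studies". Section 4.3.8 adds: "For summaries of shift from Baseline in safety parameters, all values will be considered for these analyses". None of these rules mentions fasting.

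Appendix 1, invoked from 9.2, has two glucose blocks. One is headed as fasting glucose and crosses three Baseline categories (below 100, 100 to below 126, 126 mg/dL or more) with the same categories at Week 24. The other is headed as highest post-Baseline glucose, uses 200 and 500 mg/dL, and is not labelled fasting.

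**Sampling (protocol).** Footnote l of the Schedule of Activities says "Clinical laboratory tests at each visit include clinical chemistries and a complete blood count". Table 4 (section 6.6.2.4) includes glucose in the chemistry column: "Potassium Chloride Bicarbonate Blood Urea Nitrogen Creatinine Glucose Calcium Phosphate". Footnote l then names fasting glucose, lipids and hemoglobin A1c as additional tests at Week 24/Baseline and Week 52. Section 6.2 requires the 8-hour fast at Week 24/Baseline and Week 52/Early Termination, and continues: "Laboratory requisitions must indicate whether or not the patient was not fasted for their chemistry and lipid testing".

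**Risk (protocol 7.10, Table 6).** For metabolic changes, including insulin resistance and diabetes, the stated monitoring is: "Fasting lipids and glucose will be monitored during the study".

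**The concern.** Glucose depends on whether the patient has eaten. A column of mean changes from Baseline is interpretable only if both ends were sampled in the same state, or if the reader knows that they were not. Under the SAP as written, the columns for Weeks 28 to 48 and Follow-up may hold a mixture of fasted and fed samples, compared with a Baseline that is probably fasted, with no label to say so.

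The worst-value shift is more exposed than the by-visit means, because a single high sample fixes a patient's post-Baseline category for the whole of both studies.

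The extension has no concurrent control. All three parent groups take the same open-label treatment, so a sampling-state artefact common to all of them cannot be removed by comparison. In the former placebo group, the first scheduled visit after starting relugolix (Week 28) is also a visit without a required fast.

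The analysis that would answer the question cleanly is a fasted-to-fasted category shift at the end of treatment, and Appendix 1 does not list it. Its fasting block ends at Week 24, when the extension begins.

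**Working it through.** The documents state no figure for this point, so there is nothing to reproduce. The check is a reading of the schedule, a count, and one illustration.

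**1. Fasting requirement by visit** (Schedule of Activities, Clinical Laboratory Tests row, footnotes l and m; section 6.2)

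| Visit | Chemistry drawn | Fast required |
|---|---|---|
| Week 24/Baseline | yes | yes |
| Weeks 28, 32, 36, 40, 44, 48 | yes | none stated |
| Week 52/Early Termination | yes | yes |
| Follow-up | yes | none stated |
| Unscheduled | optional | none stated |

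Scheduled on-treatment samples after Week 24: 7. Without a fasting requirement: 6, and 6/7 = 86%. With Follow-up: 7/8 = 87.5%.

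**2. Is glucose drawn at Weeks 28 to 48?** Probably. Table 4 lists it under chemistry with no visit limit, and chemistry is drawn at each visit. It is not certain, because Table 4 also lists hemoglobin A1c, which footnote l confines to two visits, and footnote l calls fasting glucose an additional test. The separate highest post-Baseline block in Appendix 1 suggests that glucose not labelled fasting is expected. Lipids are different: footnote l schedules them in the extension only at visits with a required fast.

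**3. Is Baseline fasted?** SAP 4.3.7 defines Baseline as the last measurement before the first parent-study dose and does not mention fasting. The parent protocols are not supplied. A fasted Baseline is inferred from the fasting block in Appendix 1, which classifies patients by their Baseline value.

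**4. Which specified glucose outputs rest on a required fast?**
- By-visit change: in the extension, the Week 24 and Week 52 columns, apart from early-termination samples that fall in other windows.
- Worst-value shift: no restriction.
- Highest post-Baseline thresholds: no restriction, which suits an any-time criterion.
- Fasting category shift: Week 24 only.

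**5. Illustration of the worst-value exposure.** Let p be the chance that one sample without a required fast exceeds the upper limit in a woman with no metabolic change. The documents do not give p, so it is an assumption. If samples are independent, the chance of at least one high value in k samples is 1 − (1 − p)^k.

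| p (assumed) | k = 6 (Weeks 28 to 48) | k = 7 (plus Follow-up) |
|---|---|---|
| 1% | 1 − 0.99^6 = 5.9% | 6.8% |
| 2% | 1 − 0.98^6 = 11.4% | 13.2% |
| 5% | 1 − 0.95^6 = 26.5% | 30.2% |
| 10% | 1 − 0.90^6 = 46.9% | 52.2% |

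Repeated samples in one woman are likely to be positively correlated, which lowers these figures. If they were perfectly correlated, the chance would be p itself. At p = 5% and k = 6 the range is thus 5% to 26.5%. Fasted samples also exceed the limit at some rate, so the excess due to sampling state is smaller again.

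**The case against.** **The SAP already separates the two kinds of glucose.** Appendix 1 has a fasting block and an any-time block, so fasting status is not ignored. This stands in part. The split covers the threshold tables only and does not govern the by-visit or shift summaries in 9.2. Section 9.2 also asks for thresholds at the last on-treatment observation, which for completers should be Week 52, but the rows of the fasting block name Week 24.

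**Other evidence bears on the metabolic risk.** Hemoglobin A1c is drawn at Week 24 and Week 52 and has its own Appendix 1 thresholds (6.5 or more, and a rise above 1.0). Table 12 summarizes a hyperglycemia/new-onset diabetes query. Neither depends on a same-day fast, and glucose at Week 52 is itself fasted. This stands and limits the harm, but it does not make the mixed glucose tables readable.

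**No fasting requirement does not mean fed.** Section 5.4 has patients dose in the morning at least 1 hour before breakfast. This also stands. A reader might infer that after-meal values will be reported as glucose rises on relugolix, with means rising at Week 28 and falling back at Week 52. The documents do not support that. They show only that the samples may differ in state. The dosing rule does not settle the matter either: scheduled in-clinic dosing is only at Weeks 24 and 52, so at other visits a patient may dose at home, eat, and then attend.

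**The fasting flag may not exist at every visit.** The requisition sentence in section 6.2 directly follows the Week 24/Week 52 rule and may concern only those visits. This is fair, and the fix needs a fallback.

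**The summaries are descriptive and the rules are the same for all groups.** This is true, and it keeps the point modest. Equal rules do not help where the reading is change over time within a group.

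**Conclusion.** The point holds in a limited form. As written, SAP 9.2 and 4.3.8 combine glucose values from different, unlabelled fasting states: 6 of the 7 scheduled on-treatment extension samples after Week 24 have no required fast. Appendix 1 gives no fasting-glucose category shift at Week 52, the one later scheduled extension visit with a required fast. Unfasted values can therefore be read as rises from Baseline in the summaries of a named metabolic risk.

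This rests on two inferences: that glucose is part of the chemistry drawn at Weeks 28 to 48, and that the parent Baseline was fasted. The size of the distortion is unknown, because the documents give no fed-fasted difference. The percentages in the illustration follow from an assumed p and independence, and should not be quoted as an expected rate of false high values.

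The documents do not support the stronger reading that the metabolic risk cannot be assessed. Fasted glucose at Weeks 24 and 52, hemoglobin A1c and adverse events all bear on it. No efficacy result or formal comparison is affected. The change is worth making because it is cheap and makes the glucose tables interpretable.

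**What to change.** 1. In Appendix 1, add Week 52 to the fasting-glucose block, so that Baseline category is crossed with category at Week 24 and at Week 52.
2. In SAP 9.2, base the fasting-glucose change and shift summaries on samples recorded as fasted for at least 8 hours. First confirm that the requisition flag reaches the analysis data. If it is not available at other visits, use the nominal visits with a required fast (Week 24/Baseline and Week 52/Early Termination). Nominal visit matters here because SAP 4.3.8 assigns windows by study day, so an early-termination sample can fall in another week's window.
3. Tabulate all other glucose values separately, labelled as random or any-state, and keep the any-time criteria of 200 and 500 mg/dL on every sample, so that no safety data are dropped.
4. State the fasting status of the parent Baseline sample in the SAP.

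The cost is SAP wording before database lock, one filter and one additional table, with no new data collection. The downside is that fasting glucose in the extension is then shown mainly at Weeks 24 and 52. The separate any-state table keeps the intervening values in view.

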9.3. Other Safety Analyses

9.3.1. Electrocardiograms

ECG interval results and changes from Baseline will be summarized descriptively for each scheduled visit, including visits in both the parent study and extension study, in both tables and figures using data provided by and read by central reading.

A categorical analysis of corrected QT interval using Fridericia's calculation (QTcF) intervals will also be performed for each scheduled visit and for the maximum post-Baseline value. The

number and percentage of patients in each QTcF interval category (< 450 msec, 450 to 480 msec, 481 to 500 msec, and > 500 msec) will be summarized. Categories of changes from Baseline (≥ 30 msec and ≥ 60 msec) will be summarized as well.

ECG intervals will be presented in by-patient listing. Overall ECG assessments performed by local reading will also be listed.

9.3.2. Vital Signs

Blood pressure (systolic and diastolic), heart rate, and BMI will be summarized at Baseline and each subsequent scheduled assessment, including visits in both the parent study and extension study, by parent study treatment group. Change from Baseline will be calculated and presented for each parameter at all scheduled post-Baseline assessment time points in both tables and figures. All vital sign data will also be provided in by-patient listings.

Potentially clinically significant abnormalities in vital signs are defined in [Table 14](#), and they will be summarized by using post-Baseline values that meet the defined criteria. Potentially clinically significant abnormalities will also be flagged in by-patient listings.

Table 14: Categories of Potentially Clinically Significant Abnormalities in Vital Signs

Parameter	Category
Systolic blood pressure	≥ 140 mmHg
	≥ 180 mmHg
	≤ 90 mmHg
	Increase of ≥ 20 mmHg from Baseline Decrease of ≥ 20 mmHg from Baseline
Diastolic blood pressure	≥ 90 mmHg
	≥ 105 mmHg
	≤ 50 mmHg
	Increase of ≥ 15 mmHg from Baseline Decrease of ≥ 15 mmHg from Baseline
Heart rate	≥ 120 bpm
	< 45 bpm
	Increase of ≥ 15 bpm from Baseline
	Decrease of ≥ 15 bpm from Baseline

Abbreviations: bpm = beats per minute; mmHg = millimeters of mercury.

